#### **9.1.8.1.3 Timing of Dose Administration of Lenvatinib**

On Day 1 of each cycle, lenvatinib will be administered after completion of pembrolizumab. Lenvatinib will be taken once a day with water at approximately the same time each day for 21 days in each cycle.

The participant must be instructed in the handling of study drug as follows:

- To store the study treatment at room temperature.
- To make every effort to take doses on schedule.
- To report any missed doses.
- If the participant vomits after taking study treatment, the participant should not take another dose that day.
- To keep study treatment in a safe place and out of reach of children.
- If a dose of lenvatinib is missed by more than 12 hours, that dose should be skipped, and the next scheduled dose should be administered at the usual time.

#### **9.1.9 Withdrawal/Discontinuation**

Participants who discontinue study treatment prior to completion of the treatment period should be encouraged to continue to be followed for all remaining study visits.

When a participant withdraws from participation in the trial, all applicable activities scheduled for the final study visit should be performed at the time of withdrawal. Any adverse events which are present at the time of withdrawal should be followed in accordance with the safety requirements outlined in Section 9.3 - Adverse Events, Serious Adverse Events and Other Reportable Safety Events.

##### **9.1.9.1 Withdrawal From Future Biomedical Research**

Participants may withdraw their consent for Future Biomedical Research. Participants may withdraw consent at any time by contacting the principal investigator for the main trial. If medical records for the main trial are still available, the investigator will contact the Sponsor

using the designated mailbox ([contact]). Subsequently, the participant's consent for Future Biomedical Research will be withdrawn. A letter will be sent from the Sponsor to the investigator confirming the withdrawal. It is the responsibility of the investigator to inform the participant of completion of withdrawal. Any analyses in progress at the time of request for withdrawal or already performed prior to the request being received by the Sponsor will continue to be used as part of the overall research trial data and results. No new analyses would be generated after the request is received.

In the event that the medical records for the main trial are no longer available (eg, if the investigator is no longer required by regulatory authorities to retain the main trial records) or the specimens have been completely anonymized, there will no longer be a link between the participant's personal information and their specimens. In this situation, the request for specimen withdrawal cannot be processed.

#### **9.1.10 Participant Blinding/Unblinding**

This is an open-label trial; there is no blinding for this trial.

#### **9.1.11 Calibration of Equipment**

The investigator or qualified designee has the responsibility to ensure that any device or instrument used for a clinical evaluation/test during a clinical study that provides information about inclusion/exclusion criteria and/or safety or efficacy parameters shall be suitably calibrated and/or maintained to ensure that the data obtained is reliable and/or reproducible. Documentation of equipment calibration must be retained as source documentation at the study-site.

### **9.2 Efficacy Assessments**

#### **9.2.1 Tumor Imaging and Assessment of Disease**

All imaging will be completed and read locally. Additionally, images will be collected and stored at a central imaging vendor for potential future use. The process for image collection and transmission to the central imaging vendor can be found in the Site Imaging Manual (SIM).

Tumor imaging is strongly preferred to be acquired by computed tomography (CT). For the abdomen and pelvis, contrast-enhanced MRI may be used when CT with iodinated contrast is contraindicated, or when mandated by local practice. The same imaging technique regarding modality, ideally the same scanner, and the use of contrast should be used in a participant throughout the study to optimize the reproducibility of the assessment of existing and new tumor burden and improve the accuracy of the assessment of response or progression based on imaging. Note: for the purposes of assessing tumor imaging, the term "investigator" refers to the local investigator at the site and/or the radiological reviewer located at the site or at an offsite facility.

All scheduled images for all study participants from the sites will be submitted to the central imaging vendor. In addition, images (including via other modalities) that are obtained at an unscheduled time point to determine disease progression, as well as imaging obtained for

other reasons, but captures radiologic progression based on investigator assessment, should also be submitted to the central imaging vendor.

Participant eligibility will be determined using local assessment (Investigator assessment) based on RECIST 1.1.

#### **9.2.1.1 Initial Tumor Imaging**

Initial tumor imaging at screening must be performed within 28 days prior to the date of randomization.

Tumor imaging performed as part of routine clinical management are acceptable for use as screening tumor imaging if they are of diagnostic quality and performed within 28 days prior to the date of randomization. If brain imaging is performed to document the stability of existing metastases, MRI is preferred; however, CT imaging is acceptable if MRI is medically contraindicated.

#### **9.2.1.2 Tumor Imaging During the Study**

The first on-study imaging assessment should be performed at 9 weeks (63 days  $\pm$  7 days) from the date of randomization. Subsequent tumor imaging should be performed every 9 weeks (63 days  $\pm$  7 days) or more frequently if clinically indicated. After 1 year, participants who remain on treatment will have imaging performed every 12 weeks (84 days  $\pm$  7 days). Imaging timing should follow calendar days and should not be adjusted for delays in cycle starts. Imaging should continue to be performed until disease progression is identified by the investigator (unless the site Principal Investigator [PI] elects to continue treatment and follow iRECIST), the start of new anticancer treatment, withdrawal of consent, or death or notification by the Sponsor, whichever occurs first. All supplemental imaging must be submitted to the central imaging vendor.

Objective response should be confirmed by a repeat imaging assessment. Tumor imaging to confirm PR or CR should be performed at least 4 weeks after the first indication of a response is observed. Participants will then return to regular scheduled imaging, starting with the next scheduled imaging time point. Participants who receive additional imaging for confirmation do not need to undergo the next scheduled tumor imaging (ie, 9 or 12 weeks later) if it is less than 4 weeks later; tumor imaging may resume at the subsequent scheduled imaging time point.

Per iRECIST (Section 9.2.1.5), disease progression in participants treated with pembrolizumab should be confirmed by the site 4 to 8 weeks after site-assessed first radiologic evidence of PD in clinically stable participants. Participants who have unconfirmed disease progression may continue on treatment at the discretion of the site Investigator until progression is confirmed by the site, provided they have met the conditions detailed in Section 9.2.1.5. Participants who obtain a confirmation scan do not need to undergo the next scheduled tumor imaging if it is less than 4 weeks later; tumor imaging may resume at the subsequent scheduled imaging time point if clinically stable. Participants who have confirmed disease progression as assessed by the site will discontinue study treatment. Exceptions are detailed in Section 9.2.1.5.

### **9.2.1.3 End of Treatment and Follow-up Tumor Imaging**

For participants who discontinue study treatment, tumor imaging should be performed at the time of treatment discontinuation ( $\pm 4$ -week window). If previous imaging was obtained within 4 weeks prior to the date of discontinuation, then imaging at treatment discontinuation is not mandatory. For participants who discontinue study treatment due to documented disease progression, this is the final required tumor imaging.

For participants who discontinue study treatment without documented disease progression, every effort should be made to continue monitoring their disease status by tumor imaging using the same imaging schedule used while on treatment (every 9 weeks in Year 1 or 12 weeks after Year 1) to monitor disease status until the start of a new anticancer treatment, disease progression, death, or the end of the study, whichever occurs first.

### **9.2.1.4 RECIST 1.1 Assessment of Disease**

RECIST 1.1 will be used as the primary measure for assessment of tumor response and date of disease progression. Although RECIST 1.1 references a maximum of 5 target lesions in total and 2 per organ, the Sponsor allows a maximum of 10 target lesions in total and 5 per organ, if clinically relevant to enable a broader sampling of tumor burden.

### **9.2.1.5 iRECIST Assessment of Disease**

iRECIST is based on RECIST 1.1 but adapted to account for the unique tumor response seen with immunotherapeutic drugs. iRECIST will be used by the investigator to assess tumor response and progression and make treatment decisions. When clinically stable, participants should not be discontinued until progression is confirmed by the investigator, working with local radiology, according to the rules outlined in Appendix 8. This allowance to continue treatment despite initial radiologic PD considers the observation that some participants can have a transient tumor flare in the first few months after the start of immunotherapy, and then experience subsequent disease response. This data will be captured in the clinical database.

Clinical stability is defined as the following:

- Absence of symptoms and signs indicating clinically significant progression of disease
- No decline in ECOG performance status
- No requirements for intensified management, including increased analgesia, radiation, or other palliative care

Any participant deemed clinically unstable should be discontinued from study treatment at site-assessed first radiologic evidence of PD and is not required to have repeat tumor imaging for confirmation of PD by iRECIST.

If the investigator decides to continue treatment, the participant may continue to receive study treatment and the tumor assessment should be repeated 4 to 8 weeks later to confirm PD by iRECIST, per investigator assessment. Images should continue to be sent to the central imaging vendor for potential retrospective use.

If repeat imaging does not confirm PD per iRECIST, as assessed by the investigator, and the participant continues to be clinically stable, study treatment may continue and follow the regular imaging schedule. If PD is confirmed, participants will be discontinued from study treatment.

If a participant has confirmed radiographic progression (iCPD) as defined in Appendix 8, study treatment should be discontinued; however, if the participant is achieving a clinically meaningful benefit, an exception to continue study treatment may be considered following consultation with the Sponsor. In this case, if study treatment is continued, tumor imaging should continue to be performed following the intervals as outlined in Section 2 and submitted to the central imaging vendor.

A description of the adaptations and iRECIST process is provided in Appendix 8, with additional details in the iRECIST publication [Seymour, L., et al 2017]. A summary of imaging and treatment requirements after first radiologic evidence of progression is provided in [Table 9](#) and illustrated as a flowchart in [Figure 3](#).

[figure not shown]
Table 9 Imaging and Treatment for Clinically Stable Participants Treated with Pembrolizumab after First Radiologic Evidence of PD Assessed by the Investigator

	Clinically Stable		Clinically Unstable	
	Imaging	Treatment	Imaging	Treatment
First radiologic evidence of PD by RECIST 1.1	Repeat imaging at 4 to 8 weeks to confirm PD.	May continue study treatment at the investigator's discretion while awaiting confirmatory tumor imaging by site by iRECIST.	Repeat imaging at 4 to 8 weeks to confirm PD per investigator's discretion only.	Discontinue treatment
Repeat tumor imaging confirms PD (iCPD) by iRECIST per investigator assessment	No additional imaging required.	Discontinue treatment (exception is possible upon consultation with Sponsor).	No additional imaging required.	Not applicable
Repeat tumor imaging shows iUPD by iRECIST per investigator assessment	Repeat imaging at 4 to 8 weeks to confirm PD. May occur at next regularly scheduled imaging visit.	Continue study treatment at the investigator's discretion.	Repeat imaging at 4 to 8 weeks to confirm PD per investigator's discretion only.	Discontinue treatment
Repeat tumor imaging shows iSD, iPR, or iCR by iRECIST per investigator assessment.	Continue regularly scheduled imaging assessments.	Continue study treatment at the investigator's discretion.	Continue regularly scheduled imaging assessments.	May restart study treatment if condition has improved and/or clinically stable per investigator's discretion. Next tumor imaging should occur according to the regular imaging schedule.

iCPD=iRECIST confirmed progressive disease; iCR=iRECIST complete response; iRECIST=modified Response Evaluation Criteria in Solid Tumors 1.1 for immune-based therapeutics; iSD=iRECIST stable disease; iUPD=iRECIST unconfirmed progressive disease; PD=progressive disease; RECIST 1.1=Response Evaluation Criteria in Solid Tumors 1.1.

**Figure 3 Imaging and Treatment for Clinically Stable Participants Treated with Pembrolizumab after First Radiologic Evidence of PD Assessed by the Site**

iRECIST=Immune Response Evaluation Criteria in Solid Tumors; PD=progressive disease;  
 RECIST=Response Evaluation Criteria in Solid Tumors.

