#### **Attribution of Toxicity:**

When study interventions are administered in combination, attribution of an adverse event to a single component is likely to be difficult. Therefore, while the investigator may attribute a toxicity event to pembrolizumab monotherapy, coformulations, or IO combinations, pembrolizumab monotherapy, coformulations, or IO combinations must be held according to the criteria in the Dose Modification and Toxicity Management Guidelines for Immune-Related Adverse Events.

In these cases where the toxicity is attributed to pembrolizumab coformulations or IO combinations, re-initiation of pembrolizumab as a monotherapy may be considered after communication with and agreement by the Sponsor.

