- The participant interrupts lenvatinib administration for more than 28 consecutive days, unless approved with written documentation from the Sponsor.
- Clinical conditions described in Section 7.2 Dose Modification
- The participant has a medical condition or personal circumstance which, in the opinion of the investigator and/or sponsor, placed the participant at unnecessary risk from continued administration of study treatment.
- The participant has a confirmed positive serum pregnancy test.
- The participant has a positive urine drug screen at any time during the course of the study.
- Confirmed radiographic disease progression outlined in Section 9.2.1.4 (after obtaining informed consent addendum and Sponsor communication, the investigator may elect to continue treatment beyond disease progression).
- Any progression or recurrence of any malignancy, or occurrence of another malignancy that requires active treatment
- Noncompliance with study treatment or procedure requirements
- Any study treatment-related toxicity specified as a reason for permanent discontinuation as defined in the guidelines for dose modification due to AEs in Section 7.2.
- Completion of 35 treatments (approximately 2 years) with pembrolizumab. Combination treatment with MK-1308 or MK-4280 will be discontinued upon completion of the 35th cycle of pembrolizumab. For the lenvatinib combination arm, if a participant completes 35 infusions of pembrolizumab, they may continue with lenvatinib alone until disease progression or toxicity.

Discontinuation of treatment may be considered for participants who have attained a confirmed CR by local investigator assessment and have been treated for at least 8 cycles and received at least 2 cycles beyond the date when the initial CR was declared.

For participants who are discontinued from study treatment but continue to be monitored in the trial, all visits and procedures, as outlined in the SoA, should be completed.

Discontinuation from study treatment is “permanent.” Once a participant is discontinued, he/she shall not be allowed to restart study treatment.

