### *Assessment and Decision at RECIST 1.1 Progression*

For participants who show evidence of radiological PD by RECIST 1.1 as determined by the investigator; the investigator will decide whether to continue a participant on study treatment until repeat imaging is obtained (using iRECIST for participant management; see [Table 9](#) and [Figure 3](#)). This decision by the investigator should be based on the participant's overall clinical condition.

Clinical stability is defined as the following:

- Absence of symptoms and signs indicating clinically significant progression of disease
- No decline in ECOG performance status
- No requirements for intensified management, including increased analgesia, radiation, or other palliative care

Any participant deemed **clinically unstable** should be discontinued from study treatment at site-assessed first radiologic evidence of PD and is not required to have repeat tumor imaging for confirmation of PD by iRECIST.

If the investigator decides to continue treatment, the participant may continue to receive study treatment and the tumor assessment should be repeated 4 to 8 weeks later to confirm PD by iRECIST, per investigator assessment. Images should continue to be sent to the central imaging vendor for potential retrospective use.

Tumor flare may manifest as any factor causing radiographic progression per RECIST 1.1, including:

- Increase in the sum of diameters of target lesion(s) identified at baseline to  $\geq 20\%$  and  $\geq 5$  mm from nadir
  - o Note: the iRECIST publication uses the terminology “sum of measurements”, but “sum of diameters” will be used in this protocol, consistent with the original RECIST 1.1 terminology.
- Unequivocal progression of non-target lesion(s) identified at baseline
- Development of new lesion(s)

iRECIST defines new response categories, including iUPD (unconfirmed progressive disease) and iCPD (confirmed progressive disease). For purposes of iRECIST assessment, the first visit showing progression according to RECIST 1.1 will be assigned a visit (overall) response of iUPD, regardless of which factors caused the progression.

At this visit, target and non-target lesions identified at baseline by RECIST 1.1 will be assessed as usual.

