New lesions will be classified as measurable or non-measurable, using the same size thresholds and rules as for baseline lesion assessment in RECIST 1.1. From measurable new lesions, up to 5 lesions total (up to 2 per organ), may be selected as New Lesions – Target. The sum of diameters of these lesions will be calculated and kept distinct from the sum of diameters for target lesions at baseline. All other new lesions will be followed qualitatively as New Lesions – Non-target.

*Assessment at the Confirmatory Imaging*

On the confirmatory imaging, the participant will be classified as progression confirmed (with an overall response of iCPD), or as showing persistent unconfirmed progression (with an overall response of iUPD), or as showing disease stability or response (iSD/iPR/iCR).

*Confirmation of Progression*

Progression is considered confirmed, and the overall response will be iCPD, if ANY of the following occurs:

- Any of the factors that were the basis for the initial iUPD show worsening
  - o For target lesions, worsening is a further increase in the sum of diameters of  $\geq 5$  mm, compared to any prior iUPD time point
  - o For non-target lesions, worsening is any significant growth in lesions overall, compared to a prior iUPD time point; this does not have to meet the “unequivocal” standard of RECIST 1.1
  - o For new lesions, worsening is any of these:
    - An increase in the new lesion sum of diameters by  $\geq 5$  mm from a prior iUPD time point
    - Visible growth of new non-target lesions
    - The appearance of additional new lesions
- Any new factor appears that would have triggered PD by RECIST 1.1

*Persistent iUPD*

Progression is considered not confirmed, and the overall response remains iUPD, if:

- None of the progression-confirming factors identified above occurs AND
- The target lesion sum of diameters (initial target lesions) remains above the initial PD threshold (by RECIST 1.1)

Additional imaging for confirmation should be scheduled 4 to 8 weeks from the imaging on which iUPD is seen. This may correspond to the next visit in the original visit schedule. The assessment of the subsequent confirmation imaging proceeds in an identical manner, with possible outcomes of iCPD, iUPD, and iSD/iPR/iCR.

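### Table 9 lets a participant discontinued at unstable first progression restart study treatment, while Section 8.1 forbids any restart after discontinuation

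*Combined protocol and SAP*

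**What the plan says.** Three places set the rule for a participant who is clinically unstable when progression is first seen. The text of Section 9.2.1.5 says that such a participant "should be discontinued from study treatment at site-assessed first radiologic evidence of PD". Appendix 8 (Section 12.8) repeats it: "should be discontinued from study treatment at site-assessed first radiologic evidence of PD and is not required to have repeat tumor imaging". Table 9 has the same instruction in its clinically unstable treatment column, in the row for first radiologic PD.

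A repeat scan is optional for this participant. Table 9 describes it as "Repeat imaging at 4 to 8 weeks to confirm PD per investigator's discretion only". If it is done and shows iSD, iPR or iCR, the last row of the same column reads: "May restart study treatment if condition has improved and/or clinically stable per investigator's discretion".

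Section 8.1, which governs discontinuation for the whole study, ends by calling discontinuation from study treatment permanent. It continues: "Once a participant is discontinued, he/she shall not be allowed to restart study treatment".

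**The concern.** Two operative dosing rules give opposite answers to one question: may a participant who was stopped for progression with clinical deterioration be given the investigational combination again? Under Table 9 the investigator may decide to do so. Under Section 8.1 the same act is prohibited, and a site that relied on Table 9 would have a protocol deviation. Sites could therefore handle the same pseudo-progression case differently, each with a section of the protocol behind it.

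The wording of the permission adds a second, smaller problem. Improvement and clinical stability are joined by *and/or*, so either one is literally enough.

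**Working it through.** No arithmetic applies and the plan states no figure on this point. The check is a comparison of texts, followed by a search for anything that reconciles them.

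**1. Is it the same participant and the same act?** Yes. The restart cell sits in the clinically unstable column of Table 9, whose first row discontinues treatment. Section 9.2.1.5 and Appendix 8 describe that step as discontinuation from study treatment, which is the term Section 8.1 uses when it bars restart.

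**2. Could discontinue here mean a temporary stop?** The protocol has other words for that. Sections 7.2.1 and 7.2.1.3 and Tables 6 and 8 speak of holding, withholding or interrupting. Table 9 itself uses *discontinue* for confirmed progression, where a permanent stop is plainly meant.

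**3. Does any exception cover restart after an unstable first PD?**
- Section 8.1, progression bullet: after a consent addendum and Sponsor communication, "the investigator may elect to continue treatment beyond disease progression". This concerns continuing, it is attached to confirmed progression, and its cross-reference is to Section 9.2.1.4, not to 9.2.1.5 or Table 9.
- Section 9.2.1.2 points to exceptions in 9.2.1.5, but for confirmed progression only.
- Section 9.2.1.5 allows treatment past iCPD after Sponsor consultation. Again this is continuation.
- Appendix 8, on management after the confirmatory scan, lets treatment go on if the participant remains clinically stable. It has no restart rule.
- Section 7.2.1.1 allows that "re-initiation of pembrolizumab as a monotherapy may be considered after communication with and agreement by the Sponsor". This concerns toxicity, as do the restart provisions that follow it for immune-related events.

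None covers the case. Neither Table 9 nor Section 9.2.1.5 refers to 8.1, and no rule says which section prevails.

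**4. Can a site comply with both?** Only by never using the Table 9 permission. Every use of it breaches 8.1.

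**5. The *and/or*.** Section 9.2.1.5 defines clinical stability by three conditions: no symptoms or signs of clinically significant progression, no decline in ECOG status, and no need for intensified management. A participant whose symptoms have eased but who still needs increased analgesia has improved and is not stable. The cell as worded would permit restart.

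**6. Do the main endpoints move?** Section 10.6.1.2 dates progression at the first assessment that documents PD under RECIST 1.1, whether or not drug is discontinued, so a later restart cannot change that date. ORR is scored under RECIST 1.1, whereas the scan that opens the restart is classified under iRECIST, which serves treatment decisions and exploratory analyses. Exposure, and outcomes followed after restart, could change for an individual who restarts.

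**The case against.** The best defence is that the specific rule governs the general one. Table 9 names one situation and says what to do in it, while the 8.1 sentence is generic. The explicit radiographic trigger in 8.1 is confirmed progression, and the Table 9 participant had unconfirmed progression that then resolved. Section 9.2.1.5 says such a participant *should* be discontinued, where 8.1 says *must*. A site could reasonably follow Table 9 on this basis.

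This narrows the conflict but does not remove it. The term for stopping is the same, 8.1 separately lists any progression of a malignancy among its reasons, and its bar on restart has no qualifier. Figure 3 is not shown. If it follows Table 9, it restates the permission and leaves the bar in place.

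A reader might infer a gap in safety reporting as well. Section 9.3.1 counts its AE and SAE windows from cessation of study treatment, and if that meant the first stop, events after a restart could fall outside them. The documents do not support that reading. Section 9.10.3.1 times the Safety Follow-up Visit from the last dose, and the AE-review notes in Tables 2 and 3 also refer to the last dose. For someone who restarts, the last dose is the one after restart, and AE review is scheduled at every treatment cycle. Leaving non-serious events uncollected beyond 30 days off drug is the ordinary rule for all participants.

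Nor does the point rest on the limits for treatment interruption in Sections 7.2.1.3, 7.6 and 8.1. They concern interruptions, and each can be passed through Sponsor contact or approval.

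**Conclusion.** The contradiction is real and rests on the text alone, with no dependence on redacted figures. Any restart under Table 9 is prohibited by Section 8.1, and the *and/or* makes the permission wider than the stability criteria would suggest.

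It is minor. The number affected cannot be derived from the documents. It requires clinical instability at first PD, an optional repeat scan, resolution on that scan and an investigator who chooses to restart, so it is likely to be small and may be zero. There is no material effect on ORR or RECIST 1.1 PFS, and sample size and decision rules are untouched. What is at stake is consistent and safe conduct when re-exposing a participant who had deteriorated, and whether a site that acts on an express permission is recorded as deviating. The conclusion assumes that *discontinue* carries one meaning in Sections 8.1 and 9.2.1.5, Appendix 8 and Table 9, which is how the protocol reads.

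**What to change.** The sponsor should choose one rule and state it consistently.

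- **Option (a), keep the restart.** Add to the last sentence of Section 8.1: *except as provided in Section 9.2.1.5, Table 9, for participants whose repeat imaging shows iSD/iPR/iCR and who are clinically stable*. Change *and/or* to *and* in the Table 9 cell. This costs one clause and one word. Instead of the 8.1 clause, *hold* could replace *discontinue* for unstable participants awaiting repeat imaging. That means editing Section 9.2.1.5, Appendix 8 and Table 9, and it would bring the interruption limits into play. The *and/or* edit is needed either way.
- **Option (b), remove the restart.** Delete the restart option from the Table 9 cell. Section 8.1 then stands as written.

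Requiring Sponsor agreement or fresh consent before a restart would be a policy choice for the sponsor. It is not needed to reconcile the sections. No change to Section 9.3.1, the design, the sample size or the analysis is needed.
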